10.4.3 Ancillary Endpoint Analyses

The ancillary endpoint analysis will be conducted on the mITT Analysis Set.

- Stent movement/migration

The number and percentage of subjects who experience stent movement/migration from the start of the index procedure until completion of the 12 Month Follow-up will be summarized. Subjects with missing data will be excluded from analysis.

10.4.4 Safety Follow-up after 12 months post-procedure

AEs that started post the upper bound of 12-Month follow-up (i.e., after Day 451) will be listed.

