10.4 Primary and Secondary Endpoint Analyses.....	10
10.4.1 Primary Endpoints	10
10.4.2 Secondary Endpoints	11
10.4.3 Ancillary Endpoint Analyses.....	13
10.4.4 Safety Follow-up through 24 months post-procedure	14
10.5 Plans for Interim Analysis	14
10.6 Handling of Missing Data	14
10.7 Sensitivity Analyses	14
10.8 Subgroup Analysis.....	14
10.9 Assessment of Site Homogeneity	14
10.10 Additional Endpoint Analyses.....	14
11. Appendix: Tables, Listings and Graphs Shells	15

1. Study Design

This is a prospective, multi-center, single arm, clinical study to evaluate the safety and effectiveness of the ENTERPRISE stent when used in conjunction with endovascular coil embolization in the treatment of unruptured wide-neck, intracranial, saccular anterior circulation aneurysms (≤ 10 mm) arising from a parent vessel with a diameter of ≥ 2.5 mm and ≤ 4 mm. Due to low enrollment in the study, the Sponsor has decided to terminate the study early. The details regarding the length of follow-up for ongoing subjects are documented in the Close Out Plan.

2. Treatment Assignment

This is a single arm study with no comparator device, eligible subjects are expected to be treated with any of the following study devices.

- ENTERPRISE® Vascular Reconstruction Device and Delivery System (ENTERPRISE VRD system),
- ENTERPRISE® 2 Vascular Reconstruction Device and Delivery System (ENTERPRISE 2 VRD system).

3. Randomization and Blinding Procedures

No randomization or blinding is applied in the study.

4. Interval Windows

The following analysis intervals will be applied on the study.

Table 1: Analysis Intervals for Assessments

Visit	Description	Analysis Interval
Screening/Baseline	Screening/Baseline	Day -14 – Day 0
Immediate Pre-Procedure	Immediate prior to treatment	Within 12 hours prior to procedure
Index Procedure	Treatment	Day 0
Immediate Post-Procedure	Immediate post treatment	Within 12 hours post-procedure
Hospital Discharge	Hospital discharge	12 hours to 36 hours post-procedure
30-Day Follow-up	Telephone interview	Day 10 – Day 60
6-Month Follow-up	Clinic visit & Angiogram	Day 92 – Day 240
12-Month Follow-up	Clinic visit & Angiogram	Day 270 – Day 450
18-Month Follow-up	Telephone interview	Day 457 – Day 592
24-Month Follow-up	Clinic visit & MRA or Angiogram	Day 685 – Day 775

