5.4 Safety Follow-up after 12 Months Post-Procedure

According to the Close Out Plan, all enrolled and treated subjects will be required to complete follow-up visits through 12 months post-procedure. Hence, only a small number of subjects will have additional safety follow-up data post 12 months. AEs that started after 12-month follow-up will only be listed.

6. Levels of Significance

Protocol specified tests of hypotheses of the primary endpoints at the planned 2.5% significance level will not be conducted due to early termination of the study prior to enrollment of the planned sample size. Two-sided confidence intervals will be computed at a 95% confidence level but are not intended for inference.

7. Analysis Sets

The following analysis sets are defined for the study.

- Modified Intent-to-Treat (mITT) Analysis Set

The mITT Analysis Set consists of all consented (enrolled) subjects who meet all pre-procedure angiographic eligibility criteria, and in whom treatment with the Enterprise device is attempted.

8. Sample Size Justification

This study was originally planned at a total sample size N=320, with an interim analysis for an early stop (either due to futility or tentative success) at N=160 when subjects were enrolled and followed for a minimum of 6-month post-procedure.

However, as the study will be terminated early due to low enrollment, the total sample size for the descriptive analyses in the final CSR will be based on the actual enrollment achieved. .

9. Data and Safety Monitoring Board (DSMB)

An independent DSMB was constituted for monitoring the accumulated interim data as the study progresses to ensure subject safety. All safety review procedures were established and agreed upon in the DSMB Charter prior to enrollment of the first subject.

10. Analyses to be Conducted

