10.1 General Conventions

According to the Close Out plan, only descriptive statistics and listings will be presented, no inferential statistics will be performed for the primary and secondary endpoint. Descriptive statistics for continuous variables will include the number of subjects, mean, standard deviation, median, minimum and maximum. Descriptive statistics for dichotomous/categorical variables will include the number and percentage of subjects. All summary tables will be presented overall. Unless specified otherwise, percentages are based on non-missing values, excluding missing data and subjects who early discontinued.

- Baseline

Baseline is defined as the last non-missing measurement prior to the index procedure.

- Study Day

Unless specified otherwise, Study Day will be calculated as the difference between the event date and the date of index procedure, i.e., event date - date of index procedure. The day of index procedure is considered as Day 0.

- Date conversion

For the purposes of statistical analyses, a month is considered equivalent to 30 days and a year is considered equivalent to 360 days.

- SAS version

All statistical analyses will be performed using SAS®, Version 9.2 or later, unless otherwise noted.

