10.4.1.2 Primary Safety Endpoints

- Incidence of major ipsilateral stroke and/or death

The incidence of major ipsilateral stroke and/or death will be evaluated from the start of the index procedure until the completion of the 12-Month Follow-up based on the assessment from DSMB adjudicated data.

The number and percentage of subjects with major ipsilateral stroke and/or death up to and including 12-Month Follow-up will be summarized.

- Incidence of In-sent stenosis

The number and percentage of subjects with in-stent stenosis up to and including 12 months post-procedure will be summarized based on the assessment from the Independent Core Laboratory. Subjects with missing data will be excluded from analysis.

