10.4.2.2 Secondary Safety Endpoints

- Rate of new neurological deficits as per mRS

The number and percentage of subjects with new neurological deficits, not related to stroke or death, will be summarized at baseline (pre-procedure) and follow-up visits, e.g., 30 days, 6 and 12 months post-procedure. Subjects who died prior to an evaluation will have an mRS score of 6 imputed at that timepoint for analysis purpose.

- NIHSS total score

The NIHSS total score and its change from baseline will be summarized at baseline (pre-procedure) and follow-up visits (6 months and 12 months post-procedure). In addition, the number and percentage of subjects who show a worsening from baseline (an increase of 4 points or more) will also be presented. Only the observed scores will be included in summaries.

- Adverse Events and Clinical Complications

AEs from the start of the index procedure until completion of the 12-Month Follow-up will be coded using the latest version of Medical Dictionary for Regulatory Activities (MedDRA) into system organ class (SOC) and preferred terms (PTs). The number of events, the number and percentage of subjects with events and event rates by SOC and PT will be summarized for the following:

- Any AEs
- Study device or procedure related AEs
- Any serious AEs (SAEs)
- Unanticipated AEs
- AEs leading to death

AEs related to device/procedure are defined as those with the relationship of definitely, probably or possibility related. AEs with miss relationship will not be imputed. Subjects with multiple relationships on the same AE will be reported by the events of the highest relationship. Only the relationship as determined by CEC will be used in the safety analysis.

In addition, device or procedure related AEs will be presented overall and by study period as follows:

Table 2: AEs by Study Period

Study Period	Lower Bound of AE Start Date	Upper bound of AE Start Date
Peri-procedure	from the beginning of the procedure	Until 24 hours post-procedure (Day 0)
12-Month Follow-up	After 24 hours post-procedure (i.e., from Day 1)	Until the date of: 
○ early discontinuation in the study; or

Study Period	Lower Bound of AE Start Date	Upper bound of AE Start Date
		
 ○ the upper bound of the 12-Month analysis window (i.e., Day 450)

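### The SAP does not give the 12-month safety period one defined end: an AE starting on Day 451 falls between two outputs, and the end of the stroke/death period is not tied to a day

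*SAP*

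**What the plan says.** The SAP describes the end of the 12-month safety period in several places. Study days count from the index procedure as Day 0 (SAP 10.1).

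- **SAP Section 4, Table 1** gives the 12-Month Follow-up an analysis window of "Day 270 – Day 450".
- **SAP 10.4.2.2, Table 2** closes the 12-month AE period at early discontinuation or at "the upper bound of the 12-Month analysis window (i.e., Day 450". The lead-in sets its scope: "device or procedure related AEs will be presented overall and by study period as follows".
- **SAP 10.4.4** deals with later events: "AEs that started post the upper bound of 12-Month follow-up (i.e., after Day 451) will be listed".
- **SAP 5.4** deals with the same events without a day: "AEs that started after 12-month follow-up will only be listed".
- **SAP 10.4.1.2** counts major ipsilateral stroke and death from the start of the procedure "until the completion of the 12-Month Follow-up based on the assessment from DSMB adjudicated data". SAP 10.4.2.2 uses the same end for the AE summaries ("AEs from the start of the index procedure until completion of the 12-Month Follow-up will be coded"), and SAP 10.4.3 uses it for stent movement/migration. None of the three names a day.
- **In-stent stenosis** (SAP 10.4.1.2) and **thrombosis** (SAP 10.4.2.2) run through 12 months after the procedure, again with no day.

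**The concern.** The outputs that describe 12-month safety should share one end, so that each event is either summarised or listed and the tables can be reconciled. Here the two explicit bounds do not meet. The other outputs use wording that could mean the date of each subject's visit or the end of the analysis window.

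The second ambiguity touches a primary safety endpoint. The stroke/death rate will still be reported with an exact confidence interval (SAP 10.4), and enrollment was low, so one event more or less would show. The study is single-arm and unblinded. An undefined cut-off therefore leaves a choice that could be made after the events are known.

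**Working it through.** No power or error-rate figure is involved. The check assigns event days to outputs under each reading of the text.

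**1. The explicit bounds.** Table 1 and Table 2 both end at Day 450. Later than the upper bound therefore means Day > 450, which is Day 451 onward. SAP 10.4.4 states Day > 451, which is Day 452 onward, so its figure does not follow from Table 2. Days covered by neither: those with Day > 450 and Day ≤ 451, which is Day 451 alone. This holds on either reading of completion, for any visit inside the Table 1 window. The undated sentence in SAP 5.4 would have such an AE listed, but 10.4.4, which carries that sentence out, leaves it out.

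**2. Two readings of completion.**

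- *Visit date.* The protocol supports this. Its AE endpoint (Overview, 3.2.4.3 and 9.6) first uses the completion wording and then closes the second AE period at the 12-month visit or premature termination.
- *Window bound.* The SAP gives some support to this. SAP 10.4.2.2 uses the completion wording and then sets Day 450 in Table 2, and SAP 10.4.4 treats the end of follow-up as an upper bound.

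**3. Test events, with completion read as the visit date.**

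| Event (onset day / visit day) | Stroke/death rate | All-AE summary | Table 2 | 10.4.4 listing | 5.4 listing |
|---|---|---|---|---|---|
| Related major ipsilateral stroke, 400 / 340 | no | no | yes | no | yes |
| Unrelated AE, 400 / 340 | not applicable | no | no (out of scope) | no | yes |
| Related major ipsilateral stroke, 400 / 410 | yes | yes | yes | no | no |
| Related AE, 451 / 365 | not applicable | no | no | no | yes |
| Related AE, 452 / 365 | not applicable | no | no | yes | yes |

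In the first row the event is in the related-AE table but not in the primary rate or the table of all AEs, while SAP 5.4 says such events are only listed. In the second row SAP 5.4 would list the event and 10.4.4 would not.

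With completion read as Day 450, both Day 400 / Day 340 events enter the all-AE summary, and the stroke also enters the primary rate. The conflict in the first two rows disappears and only the Day 451 gap is left.

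**4. Width of the exposed interval under the visit-date reading** (450 minus visit day).

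- Visit on Day 320: 450 − 320 = 130 days
- Visit on Day 365: 450 − 365 = 85 days
- Visit on Day 410: 450 − 410 = 40 days
- Extremes of the SAP window: 450 − 270 = 180 days and 450 − 450 = 0 days

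The protocol requires the visit between Days 320 and 410 (Protocol 6.3.6 and 9.4). Counted stroke/death follow-up would therefore differ between on-schedule subjects by at most 410 − 320 = 90 days. The spread of 450 − 270 = 180 days needs visits at the edges of the wider analysis window.

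**5. After the fix.** With summaries through Day 450 and the listing from Day 451, no day is left out.

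**The case against.** The strongest reply is that only a one-day slip is proven. The parenthesis in SAP 10.4.4 restates that the AE falls after the upper bound, so Day 451 onward is plainly meant. The completion wording for stroke/death comes from the protocol's own endpoint definition (Protocol 3.2.2.1 and 9.6). SAP Section 4 says tables follow the Table 1 visits, and on that view stroke/death also ends at Day 450 and SAP 5.4 agrees with Table 2. Table 2 covers only device- or procedure-related AEs, so it does not show that all AEs run to Day 450. Hypothesis tests are dropped, the confidence intervals are not meant for inference (SAP Section 6), and SAP 5.4 expects few subjects with later data. Subjects who leave at their 12-month visit cannot have an event recorded afterwards.

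Most of this stands. The window reading is available, and the number of exposed subjects is small. It does not remove the point: the literal rule in 10.4.4 still omits Day 451, and the SAP never defines completion, while the protocol's AE periods use the visit.

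A reader might also infer a cut-off at Day 360, because SAP 10.1 says "a month is considered equivalent to 30 days and a year is considered equivalent to 360 days" and 12 × 30 = 360. The documents do not support that. The rule is a general unit conversion that no section applies to an endpoint. SAP 5.1.2 defines stenosis at the 12-Month Follow-up, and SAP 10.4.2.2 describes it that way again. The same logic would end the 6-month thrombosis count at 6 × 30 = Day 180, inside the SAP's own 6-month window of Days 92 to 240. Nor does either document say that age is derived with this conversion.

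**Conclusion.** The point holds as a defect in the SAP's operative rules, probably with a small numerical effect.

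- **Certain, on the literal text:** an AE starting on Day 451 is in neither Table 2 nor the 10.4.4 listing. The gap is exactly one day, and the event is lost from both outputs.
- **Conditional:** if completion means the visit, related events in the 40 to 130 days between an on-schedule visit and Day 450 are in Table 2 but outside the primary stroke/death rate and the all-AE summary. Unrelated AEs in that interval are in neither the all-AE summary nor the 10.4.4 listing. The protocol's AE periods support this reading, but the SAP does not force it.

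A reader might infer a proven contradiction between the primary rate and the AE tables. The documents support only an undefined term with two workable readings. How many subjects are followed beyond their 12-month visit is not stated beyond SAP 5.4's remark that they are few, and the Close Out Plan that governs follow-up is not among the documents. The effect on the reported rate therefore cannot be computed.

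**What to change.** State once in the SAP that the 12-month safety period ends at Day 450, the bound already in Tables 1 and 2, or at earlier study exit. Apply that end to stroke/death, in-stent stenosis, thrombosis, stent movement/migration and all AE summaries, whatever the date of the visit. Change 10.4.4 to list AEs starting after Day 450, that is, from Day 451, and give SAP 5.4 the same day. The month and year conversion in SAP 10.1 can stay as it is.

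The cost is SAP wording, with no new data. A few events between the visit and Day 450 may be added to the primary safety rate. Counted follow-up will still differ between subjects who leave the study at their visit and those followed longer, so the change makes the tables consistent but does not equalise follow-up. The wording should be settled before the final summaries are produced.

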10.5 Plans for Interim Analysis

According to the Study Close Out Plan, the planned interim analyses will not be conducted.

10.6 Handling of Missing Data

Unless stated otherwise, missing data will not be imputed, percentages will be based on non-missing data.

10.7 Sensitivity Analyses

Sensitivity analyses will not be performed for the final CSR.

10.8 Subgroup Analysis

Subgroup analysis will not be performed for the final CSR.

10.9 Assessment of Site Homogeneity

Assessment of site homogeneity will not be performed for the final CSR.

10.10 Additional Endpoint Analyses

Please refer to section 10.4.3.

11. Appendix: Tables, Listings and Graphs Shells

The table, listing and graph shells will be provided in a separate document. The changes to the shells do not constitute a signature requirement on the statistical analysis plan.

End of Document
